- **Hypothesis 1.** Assuming that greater THC potency leads to greater levels of intoxication, it is hypothesized that individuals who receive the higher THC strains will demonstrate significantly greater blood THC levels. *Alternatively, it may be that individuals titrate their dose based on potency so that they achieve the same blood levels, in which case blood levels of THC should not differ between the strains.*
- **Hypothesis 2.** It is hypothesized that blood levels of THC will be positively associated with greater harm on a number of variables previously shown to be associated with THC, such as diminished working memory and increased drug reward.

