### **Marijuana Administration at Home.**

Unlike other studies done in the United States to date, the proposed work will utilize a design that is observational but contains some experimental elements. Specifically, at the end of Appointment 1 (Baseline/Session 1) participants will be given instructions to purchase 3 grams of either a normally high THC strain, a medium THC strain, or a low THC strain at a dispensary (The Farm) in Boulder, Colorado. The normally high THC smoked flower strain contains 18% THC and 0% CBD and edibles can range from a low of 2.5 mg to greater than 10 mg of THC and 0 mg of CBD. **Please note the term “high” is relative given that the average potency in Colorado exceeds 18% and edibles are normally packaged in 10 mg THC doses.** The medium flower strain contains 12% THC and 0% CBD. The low flower THC strain contains 6% THC and 0% CBD. Colorado requires all strains of flower and edibles to be tested by a state licensed lab, which allows us to have a precise measure of potency to operationalize our high, medium, and low THC strains. Furthermore, the dispensary that we will work with (The Farm - see letter of support) performs cannabinoid and terpene potency testing on each batch produced. The dispensary will set aside a specific lot of the strains which will be labeled as “Strain A”, “Strain B”, and “Strain C” such that participants, dispensary staff, and research staff will be blind to which strain was purchased. Thus, 3 grams of each marijuana strain will be packaged in childproof bottles labeled as “Strain A”, “Strain B”, and “Strain C.” Our preliminary data suggests that 3 grams is sufficient for the study. [name] (co-investigator) will maintain the blind. The instruction to purchase “A” or

“B” or “C” will be urn randomized across participants such that equal numbers of male and female participants are included in the high, medium, and low conditions. The observational aspect of the design involves the instruction that participants can use as little or as much of the marijuana as they wish during the five days prior to the experimental appointment. The five-day period allows each participant to become accustomed to the strain. Subjects are prompted by email or text message to report how much was used each day using an online reporting system. On the fifth day, the research assistant calls the participant one hour prior to their appointment to remind the participant about the upcoming appointment from the research team.

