### **Power Analysis and Sample Size Requirement for Hypotheses 1 and 2**

Sample size was selected to permit analysis of the primary research questions at two-tailed alpha of .05 and power level of .80. Estimates of effect size follow Cohen (1988) and were conducted in G\*Power 3 (Faul et al., 2007). The primary analysis is the test of the strain X time interaction effects across repeated assessments of THC in the blood as well as assessments of working memory and the rewarding effects of the marijuana. To be conservative, we thus estimated an ICC of .60. Using a mixed model ANOVA design, with three groups, four assessment points, and an average ICC = .6 between assessment points, a total n=99 (33 per group) will allow us to detect an interaction effect as small as  $f=.12$ .

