### **The impact of attrition.**

It is anticipated that some attrition will occur in this population. Based on our current pilot study and previous marijuana studies, we anticipate a 10% attrition rate between Appointment 1 baseline session and Appointment 2 the experimental session, though we have not experienced and do not anticipate differential attrition by condition. Thus, to allow for attrition, we assume a 90% retention rate over the course of data collection. To adjust for this attrition rate, we will recruit  $n\approx 111$  participants ( $n=37$  per group). Our approach to power analysis and accounting for attrition is extremely conservative, in that the techniques we will utilize in data analysis use state of the art recommendations in iterating the estimation of missing data (Schafer & Graham, 2002; Little, 1988). All analyses are intent-to-treat and all available data are utilized in analyses.

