**Hypothesis 2** tests whether blood levels of THC are positively associated with diminished working memory and greater rewarding effects of the marijuana, operationalized with the DEQ. If analyses of Hypothesis 1 show that there are main effects by group suggesting that the higher THC strain results in significantly higher THC levels in the blood than the medium or low THC strains, the between-groups variable for models testing Hypothesis 2 will be group and we will include all four time points. Since participants were randomly assigned to group, this test allows for the highest internal validity in terms of causal conclusions about the effects of THC. If, on the other hand, participants titrate their own use such that there are few reliable between-groups differences, then actual blood levels of THC will become the between-groups (continuous) independent variable in tests of Hypothesis 2 and we will utilize timepoints 3-4 as the within-subjects effect of time. Our preliminary studies confirm wide variability in THC levels even among individuals using the same strain, so there will be adequate between-participant variability for these analyses. In either case, we will again use the RCR approach described above, and standard approaches to the estimation of interactions in regression (Aiken & West, 1991) in the case of a continuous IV (i.e., mean-centering prior to creation of the interaction term). In each model, the predictors will include the group variable (or continuous THC blood levels), a time variable, and their interaction.

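### Hypothesis 2 keeps the randomised strain comparison only if blood THC shows a strain main effect, a loosely defined test that the trial was not sized for, and a null result is then read as titration

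*Protocol*

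**What the plan says.** In the Protocol, the analysis section on effects of THC potency on blood levels, working memory and reward gives Hypothesis 2 two alternative models.

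- **Strain branch.** The condition starts "If analyses of Hypothesis 1 show that there are main effects by group suggesting that the higher THC strain" produces significantly higher blood THC than the others. The predictor is then randomised group, over all four times. The Protocol itself rates this version as the stronger basis for causal conclusions.
- **Blood-level branch.** The condition is "If, on the other hand, participants titrate their own use such that there are few reliable between-groups differences". Each participant's measured blood THC then becomes the continuous between-groups predictor, and only Times 3-4 are used.

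The Objectives set up the same reading: if users titrate, "in which case blood levels of THC should not differ between the strains".

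Three other statements bear on the rule:

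- The power section says "The primary analysis is the test of the strain X time interaction effects". It gives no power for a strain main effect.
- The Hypothesis 1 analysis expects no strain difference at Time 1, describes Time 2 as sober and before use, and places the differences at Times 3 and 4, with levels falling between those two. It also expects a main effect of strain.
- The attrition section says "All analyses are intent-to-treat and all available data are utilized in analyses".

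**The concern.** The choice between a randomised and an observational test of Hypothesis 2 hangs on a significance test that the trial was not sized to pass. The main effect averages blood THC over four times, at one of which no difference is expected and at another of which participants are sober. A real post-use difference is therefore diluted before it reaches the gate.

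If the gate is missed, the plan takes that as a sign that participants titrated. It then compares people by an exposure they chose themselves. The risk is that a potency effect on memory or reward goes without its randomised test, and that titration is concluded from a low-powered null, in a study meant to inform the regulation of potency.

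**Working it through.** **Inputs from the power section.** "two-tailed alpha of .05 and power level of .80"; a mixed design "with three groups, four assessment points"; ICC .6; 99 analysed (33 per group); smallest detectable interaction f = .12.

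**Assumptions, not in the Protocol.** The size of the strain difference at Times 2 and 4 relative to Time 3. Sphericity is also assumed.

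**Step 1: reproduce the stated design.** Interaction noncentrality = f² × N × m / (1 − ICC) = .0144 × 99 × 4 / .4 = 14.26, with 6 and 288 df. Power is .811, so the Protocol's figure is confirmed.

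**Step 2: turn the interaction into a main effect.** Let the strain difference over Times 1-4 follow a profile p. With the interaction fixed at f, the main effect is fB = f × mean(p) / √(mean squared deviation of p from its mean). Its noncentrality is fB² × N × m / (1 + 3 × ICC) = fB² × 396 / 2.8, with 2 and 96 df.

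Example, Time 4 half of Time 3, p = (0, 0, 1, .5): the mean is .375 and the sum of squared deviations is .6875, so fB = .12 × .375 / √(.6875/4) = .109. Noncentrality is 1.67 and power is .189.

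**Step 3: main-effect power at f = .12.**

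| Profile over Times 1-4 | fB | Noncentrality | Power |
|---|---|---|---|
| 0, 0, 1, 0 | .069 | 0.68 | .103 |
| 0, 0, 1, .5 | .109 | 1.67 | .189 |
| 0, 0, 1, 1 | .120 | 2.04 | .223 |
| 0, .3, 1, .5 | .148 | 3.11 | .323 |
| 0, 1, 1, 1 | .208 | 6.11 | .578 |

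The first three rows are the case where strains differ only after acute use. The main effect needs an f of about .265 for 80% power at n = 99.

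**Step 4: larger effects.** For the profile (0, 0, 1, .5), noncentrality grows with f². At f = .20 it is 1.666 × (.20/.12)² = 4.63, power .46. At f = .30 it is 1.666 × (.30/.12)² = 10.41, power .82.

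**Step 5: how often the two tests disagree.** In 20,000 simulated trials per profile at f = .12, the interaction was significant and the main effect was not in 63-73% of trials for the first three rows, 55% for the fourth and about 34% for the fifth.

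**Step 6: what the branches do with that outcome.** The first branch asks for main effects by group. The second asks for few reliable differences between groups. A significant interaction with a strain difference at Time 3 or 4, but no main effect, meets neither description clearly. If the gate is widened to accept that combination, it is passed in 64-67% of simulated trials for the first three rows.

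**Step 7: the models themselves.** The blood-level branch treats blood THC as a between-groups variable, yet the Protocol expects it to fall from Time 3 to Time 4, so within-person and between-person associations are mixed. The strain branch calls for all four times, but the table under Procedures schedules the DEQ, the reward measure, only at Sessions 3 and 4.

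**The case against.** A reader might infer that a real potency effect would usually be mistaken for titration and the randomised test dropped in most trials. The documents do not support that, for three reasons.

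- The value f = .12 is the smallest interaction the design can detect, not an expected effect on blood THC. No expected effect is stated, and gate power rises well above one half for larger effects.
- No single power figure can be given even at f = .12. Only Time 1 is expressly expected to show no difference. Time 2 follows five days on the assigned strain, so carry-over is possible, and the size of the Time 4 difference is not stated.
- The wording of the second branch permits a broader gate, under which the randomised comparison would be kept in roughly two thirds of trials at f = .12.

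It is also fair to say that Hypothesis 2 is worded as an association with blood THC. The fallback therefore tests it as worded, and the strain branch, which contains no blood THC, does not. The Protocol is open that the design is partly observational, and it claims strong causal standing only for the group comparison.

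These points limit the size of the problem but do not remove it. The randomised comparison is still conditional on an undefined and unpowered test. Even on the broader reading, about one trial in three with a true effect at f = .12 and no Time 2 difference would lose it. Absence of significance would still be taken as titration.

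**Conclusion.** The point holds as a defect in the decision rule. The Hypothesis 2 predictor depends on a loosely defined main effect that the trial was not sized to detect, and a likely result near f = .12 fits neither branch clearly.

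Main-effect power at f = .12 is about 10-22% if strains differ only after acute use, taking the Time 4 difference as 0-100% of the Time 3 difference. It is about 32% with a Time 2 carry-over of 30% of the Time 3 difference (Time 4 at half), and 58% with equal differences at Times 2-4. For larger interactions with Time 4 at half of Time 3 it is about 46% at f = .20 and 82% at f = .30. All figures assume n = 99, ICC .6 and sphericity.

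Independently of any power figure, the fallback compares self-selected exposure, which is at odds with the statement that every analysis is intent-to-treat, and it treats a changing blood level as a fixed between-person trait. What is at risk is the randomised causal comparison, not the test of Hypothesis 2 as an association.

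**What to change.** Delete the switch and report both analyses whatever Hypothesis 1 shows.

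1. **Randomised comparison.** For flower users randomised to strain, always report the strain comparison as the intent-to-treat test: working memory over all four sessions, and the DEQ over Sessions 3-4.
2. **Exposure association.** Always report the association of blood THC with each outcome at Sessions 3-4, labelled observational, with person-mean and within-person THC as separate terms. Edible users, who are not randomised, enter only this analysis.
3. **Titration.** Do not infer it from a non-significant main effect. Report confidence intervals for the strain differences in blood THC at Times 3 and 4. Compare reported amounts used between strains, and for flower the amount multiplied by labelled THC percentage. The data are already planned: "Subjects are prompted by email or text message to report how much was used each day".

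The cost is a change of wording and one extra model per outcome. No new data are needed.

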The Pittsburgh Sleep Quality Index (PSQI)	
 
The Pittsburgh Sleep Quality Index (PSQI) is an effective instrument used to measure the quality and patterns of sleep. It differentiates “poor” from “good” sleep by measuring seven domains: subjective sleep quality, sleep latency, sleep duration, habitual sleep efficiency, sleep disturbances, use of sleep medication, and daytime dysfunction over the last month. The client self rates each of these seven areas of sleep
 
	
Cold Presser Task	
 
Participants immerse their hand in cold liquid and withdraw their hand from the liquid (pain tolerance) and the timing is recorded. There is a risk of discomfort.
 
	
Session 2 & 3		
Exercise Cognitions	
 
This measure will be used to examine the acute cognitive effects of cannabis consumption on participants’ exercise cognitions, specifically exercise intentions, motivation, and self-efficacy. These measures are slight variations of assessments of exercise cognitions used in our prior work (Bryan & Rocheleau, 2002).
 
	
Session 3 & 4		
The Drugs Effects Questionnaire (DEQ)	
 
The Drug Effects Questionnaire (DEQ) is a 5 items visual analog scale used to measure the strength of marijuana as well as the desirable effects (de Wit & Phillips, 2012).
 
	
The Addiction Research Center Inventory	
 
The Addiction Research Center Inventory (ARCI; Martin, Sloan, Sapira, & Jasinski, 1971), including the ARCI—Marijuana (M) scale (Chait, Fischman, & Schuster, 1985) will be used to measure subjective effects of marijuana in addition to drug-induced euphoria, stimulant-like effects, intellectual efficiency and energy, sedation, dysphoria, and other somatic effects.
 
	
Session 4		
Cold Presser Task		

 
Participants immerse their hand in
 
		

cold liquid and withdraw their hand from the liquid (pain tolerance) and the timing is recorded. There is a risk of discomfort.		
Assessment of Blind and Potency of Marijuana	
 
At the end of the experimental session, participants will be asked to guess which strain they received and to guess the potency of THC and CBD in that strain.
 
	

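### The DEQ reward measure is scheduled only at Sessions 3 and 4, so the four-time-point Hypothesis 2 model and the four-assessment detectable effect of f=.12 do not apply to reward

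*Protocol*

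**What the plan says.** Protocol section IV, *Effects of THC Potency on THC Blood Levels, Working Memory, and Reward*, names the DEQ as the measure of reward for Hypothesis 2 and sets out two branches.

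- **Group branch.** If Hypothesis 1 shows that strain separates blood THC, "the between-groups variable for models testing Hypothesis 2 will be group and we will include all four time points". No exception is made for reward.
- **Blood-level branch.** If participants titrate and the groups converge, blood THC becomes the predictor and only time points 3 and 4 are used.

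In either branch the predictors are group (or blood THC), time and their interaction. The text refers back to the random coefficient approach set out for Hypothesis 1, which includes a quadratic time effect.

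Section XII, *Procedures*, describes the reward instrument: "The Drug Effects Questionnaire (DEQ) is a 5 items visual analog scale used to measure the strength of marijuana". It stands under the heading for Sessions 3 and 4. The block for all four sessions lists the blood draw, heart rate, the neurocognitive battery, craving and the POMS, but not the DEQ.

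Section IV, *Power Analysis and Sample Size Requirement for Hypotheses 1 and 2*, names what its primary analysis tests: "strain X time interaction effects across repeated assessments of THC in the blood as well as assessments of working memory and the rewarding effects". It works at "two-tailed alpha of .05 and power level of .80" and gives one sensitivity figure, f=.12, for three groups, four assessments, ICC .6 and 99 participants.

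**The concern.** The protocol itself fixes the reward instrument, its sessions and the model's time points, and these conflict. The DEQ has no values at Times 1 and 2 by design, so the planned missing-data methods have nothing to recover. The ARCI is also given only at Sessions 3 and 4, so it is no four-point substitute.

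Two consequences follow for one of the three outcomes named in the primary analysis.

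- **The meaning of the test changes.** With only two post-use occasions, strain x time asks whether reward fades at different rates between Session 3 and Session 4. Hypothesis 2 asks whether reward is greater with more THC.
- **The stated sensitivity was worked out for a design that reward does not have.** A null reward result would be credited with more power than the study provides.

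The affected branch is the one that the protocol itself prefers for causal conclusions, because it rests on random assignment. Unless the text is reconciled, the analyst has to choose the occasions, the time terms and the decisive test for reward after the data are in.

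**Working it through.** **Inputs.** All from the power section: k=3 groups, m=4 assessments, ICC ρ=.6, N=99 (33 per group), two-tailed alpha .05, power .80, f=.12. From the instrument table: m=2 for the DEQ. Assumed, because the protocol gives none: sphericity, which matters only for m=4.

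**Formula.** Repeated-measures ANOVA, within-between interaction, in the G*Power convention: λ = f²·N·m/(1−ρ), with df (k−1)(m−1) and (N−k)(m−1), and power from the noncentral F distribution.

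**Step 1: reproduce the stated figure (m=4).**
λ = .0144 × 99 × 4 / .4 = 14.26, df 6 and 288. Power at f=.12 is .811, and the smallest f detectable with 80% power is .119. The stated f=.12 is therefore right for outcomes measured four times.

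**Step 2: the DEQ schedule (m=2), all else unchanged.**
λ = .0144 × 99 × 2 / .4 = 7.13, df 2 and 96. Power at f=.12 is .649, and the detectable f is .142. Detecting f=.12 with 80% power would take N=137, or 138 in three equal groups. With all 111 recruits retained, power is .70.

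**Step 3: range over the ICC.** The .6 is the protocol's average between assessments, not a DEQ value for two readings about an hour apart.

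| ICC (assumed) | Two-session interaction power at f=.12 | Detectable f |
|---|---|---|
| .5 | .55 | .158 |
| .6 | .65 | .142 |
| .7 | .78 | .123 |

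At ICC .8 the power would be .92, so the shortfall depends on the two DEQ readings not being that highly correlated.

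**Step 4: which terms can be estimated.** Group crossed with intercept, linear time and quadratic time has 3 × 3 = 9 columns. With four time points the rank is 9. With Sessions 3 and 4 only there are 3 × 2 = 6 cells and the rank is 6, so the quadratic terms cannot be estimated. Group crossed with intercept and linear time has 6 columns and rank 6, so that model can be fitted.

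**Step 5: what the interaction tests.** Suppose the high strain raises the DEQ by the same amount d at both sessions. The difference from another strain is d at Session 3 and d at Session 4, so the interaction is d − d = 0, while the strain effect averaged over the two sessions is d. The hypothesis is true, yet the interaction does not see it.

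**Step 6: sensitivity of the strain main effect over the two sessions.** λ = f²·N·m/(1+(m−1)ρ), df 2 and 96. At f=.12, λ = .0144 × 99 × 2 / 1.6 = 1.78 and power is .20. The detectable f is .283. If the DEQ were given at all four sessions, the same formula would give a detectable f of .265 and power .22.

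**The case against.** **The reduced model would still run.** The listed predictors are group, time and their interaction. On two sessions that model is full rank, and the mixed-model software would fit it. This stands. A reader might infer that reward cannot be modelled at all, and the documents do not support that. What fails is the four-time-point specification and any quadratic term. That term is introduced for Hypothesis 1 and reaches Hypothesis 2 only through the reference back to the same approach.

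**The strain effect is already in the model.** This also stands: group is among the predictors. But the power section makes the strain x time interaction the primary analysis for reward too, and nothing names the averaged strain effect as the decisive reward test.

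**The other branch already works.** Correct. The blood-level branch uses time points 3 and 4, which matches the DEQ schedule, and the protocol says that its pilot data suggest titration. The contradiction touches one outcome in one branch, although that is the branch relying on randomisation.

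**The size must not be inflated.** A reader might set the main-effect figure of .28 against .12 and infer that the schedule makes reward more than twice as hard to detect. That compares two different tests with different error terms. Even with four DEQ sessions the main-effect figure would be .265, so losing Sessions 1 and 2 moves it only to .283. The loss due to the schedule is the interaction figure: detectable f from .119 to .142.

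**Conclusion.** The inconsistency is real and limited in scope. In the group branch of Hypothesis 2, the reward model is specified on four time points although its outcome exists at two. The f=.12 in the power section does not apply to reward. For the two-session interaction at N=99 and ICC .6, power at f=.12 is .65 rather than .81, and the detectable f is .142. Over an assumed ICC of .5 to .7, power is .55 to .78. The .81 assumes sphericity; the two-session figures do not need it. Blood THC and the cognitive battery are taken at all four sessions, so f=.12 stands for them on its own inputs. The interaction left for reward is also not a test of whether reward is greater; the strain effect over the two sessions is.

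**What to change.** - **Hypothesis 2 analysis text (section IV).** State that the DEQ is analysed at Sessions 3 and 4 in both branches, with no quadratic time term. State that in the group branch the strain effect averaged over the two sessions is the test of whether reward is greater. That effect is already a term in the planned model.
- **Power section (section IV).** Limit f=.12 to the outcomes measured at four sessions, and give reward a figure matched to its test: about f=.14 for the two-session interaction, or about f=.28 for the 2-df strain main effect. If a 1-df ordered-potency contrast were chosen instead, .28 would be the wrong figure; about .25 would apply if the contrast carried the whole effect.

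The cost is a text change. No visit, procedure or sample size has to change. The downside is that the stated sensitivity for reward becomes less favourable.
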